3.10.1 Procedures for discontinuation of a subject from investigational product

At any time, subjects are free to discontinue investigational product or withdraw from the study (ie, investigational product and assessments – see Section 3.11), without prejudice to further treatment. A subject that decides to discontinue investigational should always be asked about the reason(s) and the presence of any adverse events.

All patients must be administered the first dose of IP. If the patient misses the first IP administration they must be discontinued from the study and should return for IPD visit. If the patient receives the first IP administration but misses both the 2nd and the 3rd dose they must be discontinued from the study and should return for the IPD visit. If the patient receives the first IP administration but misses either the 2nd or 3rd dose they need not discontinue from the study

All patients who prematurely discontinue investigational product should return to the study center and complete the procedures described for the premature IP Discontinuation (IPD) visit within 4 weeks \pm 3 days after the last dose of IP. At that visit, although no longer on IP, patients should be encouraged to remain in the study to complete all subsequent study visits, procedures, and assessments. Note that in this case, the IPD visit replaces the nearest regular visit while the following visits continue as possible

If the patient is not willing to participate further in the study after the IPD visit, the patient should still return for a follow up visit 8 weeks \pm 3 days after the last dose of IP for final study-related assessments.

The reasons for premature discontinuation of IP should be recorded in the eCRF.

¹ Patient is considered lost to follow up when any of the following attempts of contact are failed: 3 attempts of either phone calls, faxes or emails; having sent 1 registered letter/certified mail; or 1 unsuccessful effort to check the vital status of the patient using publicly available sources, if allowed by local regulations.

If a subject is withdrawn from study, see Section 3.11.

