8.5 Methods for statistical analyses

Demographics and subject characteristics will be summarized by treatment group using frequency and percentages (for categorical variables) and descriptive statistics of mean, standard deviation, minimum, median and maximum (for continuous variables) using the full analysis set.

The analysis of the primary and secondary endpoints will include all data captured during the 84-day treatment period, including follow-up (where applicable), unless the patient withdraws consent to study participation, regardless of whether study treatment was prematurely discontinued, or delayed, and/or irrespective of protocol adherence. To emphasize the importance of collecting complete primary and secondary outcome data in all patients, the informed consent form (ICF) form will ask that patients continue study assessments for the whole 84-day double-blind treatment period, including follow-up, even if they discontinue study treatment prematurely.

Descriptive statistics will also be provided for safety and efficacy data. Unless otherwise stated, the data analysis include subjects in the full analysis set. Descriptive statistics on continuous variables will be summarized by treatment group using mean, standard deviation, minimum, median and maximum, while categorical data were summarized using frequency counts and percentages. When data are summarized by time, the values recorded against the scheduled time points listed in the protocol will be used. When assessing minimum/maximum increases or decreases during the study, all assessments, including unscheduled assessments will be used. For analysis assessing change from baseline, only subjects with both baseline and at least 1 evaluable post-baseline measure will be included.

Given there is a single primary endpoint and treatment comparison no formal testing strategy will be used for the analysis in this study.

The prior medications, categorized according to the WHO Drug Reference List dictionary which employs the Anatomical Therapeutic Chemical (ATC) classification system, will be summarized by treatment group as frequency and percentage of subjects reporting usage.

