**Table 1 Visit windows for assessments**

Adjusted defined windows visit	Scheduled study day	Maximum windows
Week 0 (Day 0)	1	Study Day=1
Day 3	4	$2 \leq \text{Study Days} \leq 5$
Day 7	8	$6 \leq \text{Study Days} \leq 11$
Day 14 (Week 2)	15	$12 \leq \text{Study Days} \leq 22$
Day 28 (Week 4)	29	$23 \leq \text{Study Days} \leq 42$
Day 56 (Week 8)	57	$43 \leq \text{Study Days} \leq 70$
Day 84 (Week 12/EOT)	85	$71 \leq \text{Study Days} \leq 98$
Day 112 (Week 16/Follow-up)	113	$99 \leq \text{Study Days}$

For assignment of data to adjusted analysis-defined visit windows, study day will be defined as follows: (Date of assessment – date of randomization) +1

For example, by this definition, the day of randomization will be Study Day 1 and the planned date of Week 4 will be Study Day 29 (=28+1).

If multiple assessments are recorded within a single visit window, please refer to the rules below:

- If there are 2 or more observations within the same visit window, then the non-missing one closest to the scheduled visit will be used in the analysis.
- If 2 observations are equidistant from the scheduled visit, then the non-missing observation with the earlier collection date will be used in the analysis.
- If 2 observations are collected on the same day, then the non-missing one with the earlier collection time will be included in the analysis.

If a visit window does not contain any observations, then the data will remain missing.

For pre-BD FEV1 (L) and body plethysmography data, the non-missing value with acceptable quality (acceptable or borderline quality grade) which is closest to the scheduled visit will be included in the analysis. For post-BD FEV1, the highest value with acceptable quality from the same date as the pre-BD FEV1 result will be used.

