##### **4.2.4.2 Study treatment compliance**

Study treatment compliance will be summarized by treatment group for the FAS and calculated as:

$$\text{Study treatment compliance} = (\text{total doses administered} / \text{total doses expected}) \times 100.$$

Patients who received no study treatment will have zero compliance. Total number of doses expected includes all visits with protocol scheduled IP administration on or before a subject's IP discontinuation or treatment complete date.

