#### *Missing data descriptions*

Tabular summaries for the percentage of patients by the reason for discontinuation of randomized treatment as well as for withdrawal from the study will be presented by treatment to describe why patients discontinue from randomized treatment or withdraw from the study. The time to discontinuation of randomized treatment and withdrawal from the study will be presented using Kaplan Meier plots (overall and split by treatment related/not treatment

related reason for discontinuation, as defined in Tables 1 and 2). Dependent on these outputs additional exploratory analyses may be produced as deemed necessary to further understand the pattern of missing data.

Primary analysis under the Treatment Policy Estimand using the Missing at Random assumption

The primary analysis of the pre-BD FEV1 is under the treatment policy estimand which allows for differences in outcomes over the entire study treatment period to reflect the effect of initially assigned randomized treatment as well as if subsequent treatments are taken. This primary analysis includes all data until patients withdraw from the study regardless of if they discontinue from randomised treatment. The Mixed Model Repeated Measures model (MMRM) used is a direct likelihood approach (DL) which is valid under the Missing at Random (MAR) assumption.

Sensitivity analysis under the Treatment Policy Estimand using both MAR and MNAR assumptions

To examine the sensitivity of the results of the primary analysis to departures from the underlying assumptions, sensitivity analyses of the repeated measures analyses will be performed for the pre-BD FEV1 using controlled sequential multiple imputation methods based on pattern mixture models, as described in the European Medicines Agency Guideline on Missing Data in Confirmatory Clinical Trials ([EMA 2010](#)). As with the primary analysis, the sensitivity analyses include all data until patients withdrew from the study regardless of if patients discontinue from randomised treatment.

The imputation process consists of a sequence of multiple imputation (MI) steps, where each step is intended to impute missing values at 1 timepoint only. This model will assume that some pre-specified subset of patients who withdraw from the study have correlations with future (unobserved) visits similar to patients in the placebo arm. This allows us to assess various deviations from the MAR assumption.

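### Protocol 3.10.1 takes patients who miss doses 2 and 3 out of the study, against its own next paragraph and Section 8.5, and can lose their Day 84 FEV1

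*Protocol*

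**What the plan says.** Protocol 3.10.1 sets three rules by dose. A patient who misses dose 1 leaves the study. A patient who misses only one of doses 2 and 3 may stay. A patient who has dose 1 and then "misses both the 2nd and the 3rd dose they must be discontinued from the study" is also to return for the IP discontinuation (IPD) visit. The section's opening explains what leaving means: patients may "withdraw from the study (ie, investigational product and assessments", so leaving the study ends the measurements as well as the drug.

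The next paragraph covers everyone who stops IP early, without exception. They are to "complete the procedures described for the premature IP Discontinuation (IPD) visit within 4 weeks" (± 3 days) of the last dose, and at that visit "patients should be encouraged to remain in the study to complete all subsequent study visits, procedures, and assessments". The IPD visit then replaces the nearest regular visit.

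Protocol 8.5 analyses all data from the 84-day period, whether or not treatment stopped, unless consent is withdrawn. It says the consent form will ask that "patients continue study assessments for the whole 84-day double-blind treatment period, including follow-up, even if they discontinue study treatment prematurely".

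SAP Appendix 8.1 adopts a treatment-policy estimand that "allows for differences in outcomes over the entire study treatment period to reflect the effect of initially assigned randomized treatment", and uses data until study withdrawal. Its table of withdrawal reasons drives the dropout-reason-based multiple imputation (DRMI). A footnote to that table counts two consecutive missed doses as a study-specific discontinuation criterion, a row that DRMI imputes from placebo. The study-specific criteria in Protocol 3.10(g) do not mention missed doses. Of the visit windows, SAP 2.2.2 says: "If a visit window does not contain any observations, then the data will remain missing".

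**The concern.** A site with a patient who has had only dose 1 has two instructions: a mandatory one to remove the patient and a general one to keep the patient attending. Following the mandatory one ends FEV1 measurement because of non-adherence, which is the kind of post-randomization event a treatment-policy estimand is meant to follow through.

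The value at risk is Day 84 pre-bronchodilator FEV1. Days 28, 56 and 84 form the average that decides whether the study is positive. A missed Day 84 measurement cannot be recovered later, yet the visit is already in the schedule. The primary mixed model would treat the gap as missing at random, and so would predict Day 84 for a patient who had one dose from patients in the same arm who mostly had three.

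**Working it through.** **1. Which visit is at risk.** Take dose 1 on Day 0, the day of randomization; SAP study day = day + 1.

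- Dose 3 is due on Day 56 ± 3, that is Days 53-59. Read strictly, the rule cannot be met before then, so the primary-contrast value it threatens is Day 84.
- SAP windows: Day 28 = study days 23-42; Day 56 = 43-70; Day 84 = 71-98.
- IPD visit on schedule: no later than 4 weeks + 3 days after dose 1 = Day 31 = study day 32. This falls in the Day 28 window.
- The 8-week follow-up visit, for patients unwilling to continue after IPD: Days 53-59 = study days 54-60. This falls in the Day 56 window.
- A patient first caught by the rule when dose 3 is missed is already past the Day 31 limit, so any IPD visit is late. On study days 60-70 it counts towards Day 56. On study days 71-98 it supplies Day 84, given that Protocol Table 3 appears to schedule spirometry at IPD (the table is broken in the text available). The protocol does not plan for this.

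**2. The plan's own power figure.** Inputs from Protocol 8.2: 115 per arm, SD 375 mL, within-subject correlation 0.6, effect 138 mL, two-sided alpha 0.05.

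- SE of the three-visit average difference = √[(2/115) × 375² × (1 + 2 × 0.6)/3] = 42.35 mL.
- Power = Φ(138/42.35 − 1.96) = 90.3%, against a stated 90% or so. Reproduced.

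**3. Ceiling per removed benralizumab patient.** Suppose the true Day 84 effect in that patient is zero. Under missing at random, the model predicts Day 84 from the arm mean and the patient's five earlier visits. With correlation 0.6, each earlier visit has weight 0.6/(1 + 4 × 0.6) = 0.176, in total 0.882. The overstatement of the three-visit average is the credited Day 84 effect divided by 3 × 115 = 345.

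| Patient's response before Day 84 | Credited effect (mL) | Overstatement (mL) |
|---|---|---|
| Full through Day 56 | 138 | 0.40 |
| Full, but gone by Day 56 | 138 × (1 − 0.176) = 113.6 | 0.33 |
| Half throughout | 138 − 0.882 × 69 = 77.1 | 0.22 |
| None | 138 × (1 − 0.882) = 16.2 | 0.05 |

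The top row is 0.40/42.35 = 0.9% of the SE. Solving the generalized least squares equations for expected values gives the same four figures.

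**4. Scaling up (assumed rates).** The documents give no missed-dose rate. Assume a share q = 2-8% of the arm misses both doses, and a share r of those would still have attended Day 84. At the ceiling the overstatement is q × r × 138/3:

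| r | Patients (115 × q × r) | Overstatement (mL) |
|---|---|---|
| 25% | 0.6-2.3 | 0.2-0.9 |
| 50% | 1.2-4.6 | 0.5-1.8 |
| 100% | 2.3-9.2 | 0.9-3.7 |

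**5. Both arms.** The rule applies to placebo too. Equal rates with equal shortfalls cancel. With 8% on benralizumab and 2% on placebo, all recoverable and at the ceiling, the shift is (0.08 − 0.02) × 138/3 = +2.8 mL. With the rates reversed it is −2.8 mL. With half recoverable it is ± 1.4 mL.

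**6. Precision.** With Day 84 missing for 4% or 8% of both arms, and six correlated visits in the model, the SE is 42.41 or 42.48 mL and power is 90.2% or 90.1%.

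**The case against.** **The sentence may be deliberate.** Section 3.10.1 separates one missed dose from two, which looks like a minimum-exposure threshold, and a specific rule can override a general one. Missing doses might also be distinct from discontinuing IP: SAP 4.2.4.2 points that way, since "Total number of doses expected includes all visits with protocol scheduled IP administration on or before" the IP discontinuation or treatment completion date. On that reading there is no strict contradiction. But two patients with the same single dose would then be followed differently: the one recorded as stopping IP stays, and the one who skips both doses is removed. No reason is given for this, and Section 8.5 makes no exception for either.

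**The SAP anticipates this group.** This stands in part. The Appendix 8.1 footnote sends two consecutive missed doses to placebo-based imputation. That is a sensitivity analysis, however, and it depends on the reason recorded. Severe non-compliance would also lead to placebo, loss to follow-up would not, and patient decision is settled by review before unblinding. The footnote classifies a withdrawal once it has happened; it does not reconcile the protocol's two instructions.

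**Day 84 is not always lost.** This stands. A reader might infer that no other visit can fill the window, but a late IPD visit on study days 71-98 would. Patients who had already withdrawn or been lost lose nothing through this rule.

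**The effect is negligible.** On size, this stands.

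**Conclusion.** The two instructions conflict as written, and enforcing the mandatory one can discard Day 84 FEV1 from patients willing to give it. The change should be made because the instructions disagree and the loss is avoidable, not because of the size of any bias.

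The size is at most about 0.40 mL per removed benralizumab patient, with power staying at about 90%. That ceiling assumes the design effect of 138 mL, full response through Day 56 and no remaining effect at Day 84. The 2-8% and 25-100% ranges are assumptions.

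Three stronger readings are not supported:

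- *That the rule biases the trial towards benralizumab.* It applies to both arms, and neither the rates nor the reasons for missing doses are known. Protocol 7.2, for example, postpones dosing during an exacerbation, which can happen in either arm.
- *That the primary analysis breaks the SAP.* Its operational rule is to use data until study withdrawal, and that is kept. The tension is with the wording about the entire treatment period.
- *That these patients drop out of the analysis.* They stay in the full analysis set, and their earlier visits still enter the model.

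**What to change.** In Protocol 3.10.1, replace the sentence on missing both later doses with, for example:

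> *A patient who has had dose 1 and misses doses 2 and 3 is given no further IP. The patient completes the IPD visit, which takes the place of the nearest regular visit, and then attends every remaining scheduled visit through Day 84 and follow-up unless consent is withdrawn.*

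This keeps the IPD instruction and changes no treatment decision, because no doses remain.

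In SAP Appendix 8.1, edit the footnote to the withdrawal-reason table so that missed doses are a reason for stopping IP and not for leaving the study, with DRMI applied only to patients who actually leave. Otherwise the footnote would describe a withdrawal criterion that the protocol no longer has.

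The cost is one protocol sentence (an amendment if made after approval) and one SAP footnote. The Day 84 and follow-up visits are already scheduled.

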3.11 Criteria for withdrawal

3.11.1 Screen failures

Screen failures are patients who do not fulfil the eligibility criteria for the study, and therefore must not be randomized. These patients should have the reason for study withdrawal recorded as ‘Incorrect Enrolment’ (ie, patient does not meet the required inclusion/exclusion criteria). This reason for study withdrawal is only valid for screen failures (not randomized patients).

3.11.2 Withdrawal of the informed consent

Patients are free to withdraw from the study at any time (investigational product and assessments), without prejudice to further treatment.

A patient who withdraws consent will always be asked about the reason(s) and the presence of any adverse events (AE). The Investigator will follow up AEs outside of the clinical study.

If a subject withdraws from participation in the study, then his/her enrolment/randomization code cannot be reused. Withdrawn subjects will not be replaced.

3.12 Discontinuation of the study

The study may be stopped if, in the judgment of AstraZeneca, trial subjects are placed at undue risk because of clinically significant findings that:

- meet individual stopping criteria or are otherwise considered significant
- are assessed as causally related to study drug,
- are not considered to be consistent with continuation of the study

Regardless of the reason for termination, all data available for the subject at the time of discontinuation of follow-up must be recorded in the CRF. All reasons for discontinuation of treatment must be documented.

In terminating the study, the Sponsor will ensure that adequate consideration is given to the protection of the subjects’ interests.

4. STUDY PLAN AND TIMING OF PROCEDURES

Table 2 Study plan - Run-in period; Visit 1 to Visit 3

Assessment/Activity	Refer to	Enrolment	Run-in	
		Visit 1	Visit 2	Visit 3
		D -35	D -21 (+/-2 days)	D -7 (+/- 2 days)
General procedures:				
Informed consent	10.4	X		
Inclusion/exclusion criteria	3.1/3.2	X	X	X
Demographics	4.1.1	X		
Medical and asthma history	4.1.1	X		
Patient Reported Outcome assessments:				
ACQ-6	5.3.2.1	X ^c		
Safety assessments:				
Complete physical examination	5.2.2.1/5.2.2.2	X		
Vital signs	5.2.4		X	X
Weight, height, BMI	5.3.1	X		
ECG	5.2.3.1	X		
Adverse events	6	X	X	X
Concomitant medication	7.7/3.9.1/3.9.1.1	X	X	X
Laboratory assessments:				
Clinical chemistry	5.2.1	X		
Hematology	5.2.1	X		
Urinalysis	5.2.1	X		
Serum pregnancy test	5.2.1.1	X		
Serology (Hepatitis B, C, HIV-1, HIV-2)	5.3.3.1	X		
FSH	5.2.1.1	X ^b		
Lung function assessments:				

Table 2 Study plan - Run-in period; Visit 1 to Visit 3

Assessment/Activity	Refer to	Enrolment	Run-in	
		Visit 1	Visit 2	Visit 3
		D -35	D -21 (+/-2 days)	D -7 (+/- 2 days)
Exhaled NO (FeNO)	5.1.2		X	
Spirometry (Pre-BD FEV ₁)	5.1.1		X ^d	X ^d
Reversibility (post-BD FEV ₁)	5.1.1.1	X ^{e,f}	X ^{e,f}	X ^e
Sub-study assessments (if applicable):				
Whole body plethysmography	5.4.1			X

- a This analysis will be only applicable for WOCBP patients.
- b FSH test done only for female patients to confirm postmenopausal status in women <50 years who have been amenorrheic for >=12 months
- c All patients must meet ACQ6 ≥1.5 at Visit 1. If this criteria is not met the patient must be screen failed and will not be allowed to rescreen.
- d For patients in the main study and the sub-study: The Pre BD FEV₁ must be conducted at Visit 2 and at Visit 3. The Pre-BD FEV₁ criteria must be met at either Visit 2 or at Visit 3.
- e For patients in the main study: If the patient did not meet Reversibility criteria at Visit 1, further attempts may be conducted at Visit 2 and at Visit 3. Reversibility testing must be performed using the algorithm as detailed in section 5.1.1.1.
- f For patients in the Body plethysmography sub-study: If the patient did not meet the reversibility criteria (using the algorithm as per section 5.1.1.1) at Visit 1, a further attempt may be conducted at Visit 2 only.
- ACQ-6 Asthma Control Questionnaire 6; BMI Body Mass Index; FeNO Fractional exhaled Nitric Oxide; FEV₁ Forced expiratory volume in 1 sec; FSH Follicle-stimulating hormone; HIV Human Immunodeficiency virus; pre-BD pre-bronchodilator; post-BD post-bronchodilator; D Day; ECG Electrocardiogram; NO nitric oxide; V Visit; W Week; WOCBP Women of childbearing potential

Table 3 Study Plan - Randomization, treatment period, follow-up; Visit 4 to Visit 11

Assessment/ activity	Refer to	Treatment							EOT	IPD	FU	Uns ^b
		V4 (D0)	V5 (D3)	V6 (D7)	V7 (D14)	V8 (D28)	V9 (D56)	V10 (D84)				
		+1	+1	+1	+3	+3	+3	+7				
Visit window (days)^{a)}												
General procedures:												
Inclusion/ exclusion criteria	3.1/3.2/ 3.3.1/ 3.3.2	X										
Randomization	4.2/3.6	X										
Patient and clinician Reported Outcome assessments:												
ACQ-6	5.3.2.1	X ^g			X	X	X	X	X	X		
SGRQ	5.3.2.2	X				X	X	X	X	X		
PGI-S	5.3.2.3	X		X	X	X	X	X	X	X		
PGI-C	5.3.2.4			X	X	X	X	X	X	X		
CGI-C	5.3.2.4		X	X	X	X	X	X	X	X		
Safety assessments:												
Complete physical examination	5.2.2.1	X							X	X		
Brief physical examination	5.2.2.2			X		X	X	X	X	X		X ^b

Table 3 Study Plan - Randomization, treatment period, follow-up; Visit 4 to Visit 11

Assessment/ activity	Refer to	Treatment								EOT	IPD	FU	Uns ^b
		V4 (D0)	V5 (D3)	V6 (D7)	V7 (D14)	V8 (D28)	V9 (D56)	V10 (D84)	V11 (D112)				
		Visit window (days) ^{a)}											
ECG	5.2.3.1		+1	±1	±3	±3	±3	±3	±7	±7	±7	N/A	
Vital signs	5.2.4	X	X	X	X	X	X	X	X	X	X	X ^b	
Adverse events	6	X	X	X	X	X	X	X	X	X	X	X ^b	
Concomitant medication	7.7/3.9.1 /3.9.1.1	X	X	X	X	X	X	X	X	X	X	X ^b	
Laboratory assessments:													
Clinical chemistry	5.2.1	X							X	X	X		
Hematology	5.2.1	X							X	X	X		
Blood for eosinophil count ^c	5.2.1/ 3.7.1	X	X	X	X	X	X	X	X	X	X		
Total IgE	5.3.3.2	X											
Serum pregnancy ^d	5.2.1.1								X	X	X		
Urinalysis	5.2.1								X	X			
Urine pregnancy test, dipstick	5.2.1.1	X				X			X	X	X		
PK ^e	5.3.4	X	X	X	X	X	X	X	X	X	X		
ADA/nAb ^f	5.3.5.3	X							X	X	X		

Table 3 Study Plan - Randomization, treatment period, follow-up; Visit 4 to Visit 11

Assessment/ activity	Refer to	Treatment							EOT	IPD	FU	Uns ^b
		V4 (D0)	V5 (D3)	V6 (D7)	V7 (D14)	V8 (D28)	V9 (D56)	V10 (D84)				
		Visit window (days) ^{a)}										
		+1	±1	±3	±3	±3	±3	±7	±7	±7	N/A	
Lung function assessments:												
Spirometry (pre-BD FEV ₁)	5.1.1	X ^(h)	X	X	X	X	X	X	X	X		
Exhaled NO (FeNO)	5.1.2	X	X	X	X	X	X	X	X	X		
Sub-study assessments: (if applicable)												
Whole body plethysmography	5.4.1	X		X	X	X	X	X	X	X		
Randomization:												
Randomization	4.3/3.6	X										
Investigational Product administration												
Benralizumab/ placebo	7.2/7.5/ 7.6	X					X	X				

- a All visits are to be scheduled from the date of randomization, not from the date of previous visit, except for early discontinuation from IP (see Section 3.10 for details)
- b Unscheduled visits may be initiated as needed, and any additional assessments may be performed at these visits, at the discretion of the Investigator. Procedures listed in the table are mandatory for each UNS visit.
- c Blood eosinophil count will be assessed in central laboratory as a part of the hematology panel but eosinophil, basophil and monocyte count will be redacted from the reports available for investigative sites
- d This analysis will be only applicable for WOCBP patients.

Clinical Study Protocol
Drug Substance Benralizumab (MEDI-563)
Study Code **D3250C00038**
Version 1.0
Date **02** Aug 2016

- e On dosing visits PK will be collected pre-dose
- f Neutralizing antibody (nAb) testing will occur for all samples that are ADA positive. Samples that are ADA negative will not be tested for nAb.
- g The patient must have an ACQ 6 >0.75 prior to randomization. If not the patient must be screen failed and cannot be rescreened
- h Pre-BD FEV1 must be conducted 60 min (+/- 10 min) and 30 min (+/- 10 min) prior to randomization and assessed against exclusion criteria in section 3.3.2.

ACQ-6 Asthma Control Questionnaire 6; ADA anti-drug antibodies; CGI-C Clinician Global Impression of Change; D Day; ECG Electrocardiogram; FeNO Fractional exhaled Nitric Oxide; FEV1 Forced expiratory volume in 1 sec; IgE Immunoglobulin E; IPD Premature Investigational Product Discontinuation; nAb Neutralizing antibodies; NO nitric oxide; PK Pharmacokinetics; PGI-C Patient Global Impression of Change; PGI-S Patient Global Impression of Severity; pre-BD pre-bronchodilator; post-BD post-bronchodilator; SGRQ St. George's Respiratory Questionnaire; UNS Unscheduled visit; V Visit; W Week; WOCBP Women of childbearing potential

